Once the adaptation of the face-to-face follow-up to the mobile format has been verified, we will move to the limited efficacy testing (Objective 2/Specific Aim 3). A group of 40 patients that fit the inclusion criteria and have completed the informed consent process will be enrolled in the study. Participants will be enrolled in either a control group (n=20) or to the mobile surveillance group (n=20). The control group will have face-to-face follow up visits with no mobile surveillance at the appropriate time points. The mobile surveillance group (n=20) will have both face-to-face visits and additional data obtained using mobile devices. Patients in both groups will complete the same set of outcome measures. These measures will be administered at the following time points, 2, 6, 12, and 24 weeks.

Patients in the mobile surveillance group will complete an assessment using a mobile device at home during the week after their scheduled clinic visit at 2, 6, 12 and 24 weeks (see **Table 1** below). The mobile device data is in addition to data gathered at face-to-face clinical appointments, thereby adding outcome data and enhancing surveillance overall. Participants in the mobile surveillance group will take videos using the mobile devices and upload the data over the encrypted network using the My MD Anderson secure email transmission. Participants will be provided with a mobile device (or tablet) that is enabled with a mobile hot spot for data transmission. For recovery of function, video sequences will be acquired by patients performing prescribed tasks that will be used to quantify functional status according to the MSTS, ECOG, TUG, EVGS, FSST, NIH PROMIS GH Score. The participant's surgical wound will also be photographed using the mobile device. Quality of Life questionnaires and PROMIS SF v1 (Appendix G) surveys will be sent to the group for completion on their mobile device via REDCap Software or thru My MD Anderson email.

To ensure patient safety, participants in the mobile surveillance group will also engage in videoconferences at the prescribed timepoints using Vidyo or Zoom. All patient communication will be documented as follow-up notes in Clinic Station by the clinician.

Table 1. Study Design

Control Group n = 20	Mobile Surveillance Group Patients n = 20
Postoperative clinic visits	Postoperative clinic visits
2 weeks	2 weeks
6 weeks	6 weeks
12 weeks	12 weeks
24 weeks	24 weeks
Measures:	Measures:
Completion rates	Completion rates

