MSTS, TUG, ECOG, EVGS, FSST, NIH PROMIS GH	MSTS, TUG, ECOG, EVGS, FSST, NIH PROMIS GH
	Mobile device surveillance follow up (in week after clinic visit) 2-3 weeks 6-7 weeks 12-13 weeks 24-25 weeks Measures: Completion rates MSTS, TUG, ECOG, EVGS, FSST, NIH PROMIS GH + wound image + videoconference with physician to ensure safety

Specific Aim 4: Acceptability

To assess acceptability of the mobile format by patients and physicians (Objective 3/Specific Aim 4), the data collected will be used to assess:

- Patient acceptance of mobile device surveillance for data collection.
- Clinician acceptance of data collection using mobile device surveillance.
- Ability to detect relevant outcome measures, wound complication, and/or adverse postoperative.

Patients will be included in the study until 24 weeks (6 months) after surgery. Upon completion of the study, both groups of participants will complete a survey evaluating satisfaction with care and the use of the mobile devices (Appendix J). In addition, clinicians from within the department of Orthopaedic Oncology will be recruited and asked to participate in this protocol. Surgeons, physician assistants and physical therapists that have agreed to and have participated in the telemonitoring program will complete surveys (Appendix I) created by the Orthopaedic Research

PI: [name], PhD

Protocol: 2015-0966

August 21, 2018

Team. Approximately, 12 clinicians will be participating in this study. These surveys were created by the research team and were adapted from a validated survey, the RAND Health Patient Satisfaction Questionnaire (PSQ). This was originally developed by Ware, et. al.(Ware, Snyder, and Wright, 1976). PSQ-18 is a short form version that retains many characteristics of its full-length counterpart. The satisfaction surveys used for this study were modified from PSQ-18.

5.0 Informed Consent:

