Patients will be approached for participation for this study at their clinic visit. Potential subjects will be informed of their eligibility and asked if they would be interested in research participation. In the privacy of the exam room, surgeons and/or research nurse or research data coordinator will discuss all aspects of the study with potential subjects and answer any questions. Interested subjects will then be given the informed consent documents and will have enough time to read over and ask questions. Subjects will be given a copy of the informed consent and will be further instructed about the study and the elements of the consent document. The research staff and/or attending physician will be available to address any questions or concerns the subject may have. Subjects who agree to participate will sign the protocol-specific informed consent.

A research nurse, research data coordinator, or PI designee with appropriate training and experience sufficient to address issues raised by potential subjects may obtain the Informed Consent. Patients may withdraw from the study at any time. Once the patient has consented for the study, he or she will be trained on how to use the mobile device or tablet.

Once a patient has been assigned to group 2 in both the feasibility and limited efficacy phases, he/she will be trained in clinic on how to use the app for both videos and photographs by a licensed Physical Therapist. Reference guides and instruction manuals will be provided to the patient and contact information for the research team for any further assistance. The training session should take approximately 10-15 minutes per individual.

6.0 Statistics:

Feasibility Assessment

The feasibility assessment will consist of a group of 10 patients who meet the inclusion criteria. For feasibility, we are looking for inter-rater agreement on the physician assessed score (defined as less than 10% difference between MSTS scores evaluated using video v face-to-face) for a minimum number of patients (in this step, the MSTS score agreement for a minimum of 70% of the patients). If the feasibility criterion has been met, the research team will move forward to the limited efficacy testing. If feasibility criteria has not been met, the research team will identify the limitations and modify the process, enroll an additional 10 patients and repeat the feasibility assessment.

Limited Efficacy Testing

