There are two measurements for limited efficacy testing, completion rate and patient satisfaction/acceptability. Among the set of questionnaires the patients need to complete, MSTS,

PI: [name], PhD

Protocol: 2015-0966

August 21, 2018

TUG, and PROMIS are considered the most important. A patient is considered having completed the follow-up assessment if the three outcomes are documented for the 2-, 6-, 12, and 24-week evaluations. We will then report the completion rates for each group for comparison.

We will report the patient satisfaction rate using patient satisfaction surveys for both the control and the study groups. When the sample size is 20, a two-sided 95% confidence interval (CI) for completion rate or satisfaction rate using the large sample normal approximation will extend at most 0.22 from the observed rate (nQuery Advisor 7.0). When the sample size in the group is 20, the 95% CI will extend 0.30 from the observed difference in rate assuming the rate is 0.50 for one group and 0.70 for the other group. The physician satisfaction rate for using mobile devices will be reported. We will also address the economic impact for using mobile devices. Repeated measures analysis may be utilized to evaluate change over time in the completion status or questionnaire scores for each method.

7.0 Data Management and Security:

All patient-reported and task performance outcomes and clinical data (including videos/photos) gathered under this protocol will be stored in a password-protected database. Data will not be transferred to laptop computers that are removed from the institution. Identifiers (name, medical record number) will be collected but will be replaced by study numbers in the analytic file. The key linking these numbers will be retained in a locked file by the investigator.

Data (including videos/photos) using mobile devices or tables will be encrypted by the IT department securely transferred using MY MD Anderson secure email to the research team.

Only MDACC personnel designated by the Principal investigator will have access to study records/data. These personnel will be fully trained to maintain the confidential nature of the patient health information. Paper records will be stored in locked files inside a locked office. External storage will be password protected.

Study data will not be shared with any individuals or entities that are not involved in the study. These data will be used only for research purposes and for this research study.

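### The patient satisfaction survey is given once, at the end of 24 weeks, with none at early exit, so the satisfaction rate may be subject to selection bias

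*Combined protocol and SAP*

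**What the plan says.** Section 4.0, Specific Aim 4, sets the length of follow-up: "Patients will be included in the study until 24 weeks (6 months) after surgery". The next sentence places the survey: "Upon completion of the study, both groups of participants will complete a survey evaluating satisfaction with care and the use of the mobile devices (Appendix". Table 1 in the same section lists the measures for each group at 2, 6, 12 and 24 weeks and for the home assessments. It includes completion rates and the six functional and quality-of-life instruments, but no satisfaction survey at any time point.

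Section 5.0 adds: "Patients may withdraw from the study at any time". No exit survey is attached to withdrawal. Section 9.0 (adverse events) provides a phone call when videos or pictures are not sent in, but its stated purpose is to check for adverse events.

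Section 6.0, Limited Efficacy Testing, gives the survey its weight: "There are two measurements for limited efficacy testing, completion rate and patient satisfaction/acceptability". The analysis is stated in one sentence: "We will report the patient satisfaction rate using patient satisfaction surveys for both the control and the study groups". No denominator is given for that rate, and no rule for a patient without a survey. The precision statements in the same section are worked out for 20 patients per group.

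**The concern.** Acceptability of the mobile format is Objective 3 and Specific Aim 4. The patients who could say most about why the format does not suit someone are those who tried it and stopped. A mobile-group patient who finds the home videos too demanding and withdraws after the week-6 assessment has formed a view but is not asked for it. The same holds for a patient who dies at week 16 after three home assessments.

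Loss before 24 weeks is plausible in people operated on for bone metastases. Only the mobile group has the added home videos, wound photographs and videoconferences, so loss could also differ between the two groups. If patients with and without a survey differ in their views, the rate among responders is not the rate among those enrolled. A larger sample would not cure that.

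**Working it through.** **Inputs from the documents.** 20 patients per group (section 4.0, Specific Aim 3). Two-sided 95% interval by the large-sample normal approximation, with a half-width of at most 0.22 for one rate and 0.30 for a difference between rates of 0.50 and 0.70 (section 6.0).

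**Inputs not in the documents, assumed here.** The share of patients without a survey, taken as 10% to 50%, and a satisfaction rate near 80% among responders. The nearest figure in the plan is the roughly 30% of clinic patients who miss a postoperative appointment (section 2.0). That is not a dropout rate and is not used as one.

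**Step 1: reproduce the plan's figures.**

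- One rate, worst case p = 0.5: 1.96 × √(0.25/20) = 0.219, stated as 0.22.
- Difference: 1.96 × √(0.25/20 + 0.21/20) = 0.297, stated as 0.30.

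Both reproduce with all 20 patients in each group contributing.

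**Step 2: precision with fewer surveys.** Replace 20 by the number of responders n in each group. At n = 14:

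- one rate: 1.96 × √(0.25/14) = 0.262
- difference: 1.96 × √(0.46/14) = 0.355

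**Step 3: what the responders can say about all 20.** With n responders of whom s are satisfied, the rate over all 20 is at least s/20 (no non-responder satisfied) and at most (s + 20 − n)/20 (every non-responder satisfied). For n = 14 and s = 11:

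- responder rate 11/14 = 79%
- lower bound 11/20 = 55%
- upper bound (11 + 6)/20 = 85%

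| Assumed loss | Responders n | Satisfied s | Responder rate | Bounds over all 20 | Half-width, one rate | Half-width, difference |
|---|---|---|---|---|---|---|
| 10% | 18 | 14 | 78% | 70% to 80% | 0.231 | 0.313 |
| 20% | 16 | 13 | 81% | 65% to 85% | 0.245 | 0.332 |
| 30% | 14 | 11 | 79% | 55% to 85% | 0.262 | 0.355 |
| 40% | 12 | 10 | 83% | 50% to 90% | 0.283 | 0.384 |
| 50% | 10 | 8 | 80% | 40% to 90% | 0.310 | 0.420 |

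The loss of precision is modest. The gap between the bounds equals the share without a survey (6/20 = 30 points at n = 14), and data collected only at the end cannot narrow it. If non-responders hold the same views as responders, the bias is zero. The bounds allow the responder rate to be too high or too low.

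**The case against.** The strongest reply is that this is a pilot with no hypothesis test, threshold or go/no-go rule attached to satisfaction, and that early leavers are not invisible. Specific Aim 4 draws on the data collected in general, and the completion rate requires MSTS, TUG and PROMIS at all four time points, so a patient who stops shows up as a non-completer. That much stands: what is lost is survey data, and a reader who infers that leavers give no acceptability information at all goes too far. But the completion rate shows only that a patient stopped, not what the patient thought of the format.

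Three other readings are tempting and not supported.

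- **That the rate is biased toward acceptance.** The documents give no dropout rate, death rate or reasons for leaving, and death from metastatic disease need not go with dissatisfaction with a device.
- **That the stated precision is wrong.** Section 6.0 makes its half-widths conditional on a sample size of 20. They are correct on that condition and promise no number of responses.
- **That the comparison between groups pools device items which controls cannot answer.** It is true that "The control group will have face-to-face follow up visits with no mobile surveillance at the appropriate time points" and that the survey touches on device use. But Appendix J is not in the text available, and nowhere is it said that care and device items are combined into one rate.

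One could also say that study completion is not expressly tied to the 24-week visit. The sentence just before it supports that reading, and nothing in the text extends the survey to patients who leave early.

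**Conclusion.** The point holds as a design weakness that is cheap to correct. Followed as written, the plan leaves patients who withdraw or die before 24 weeks without a satisfaction survey, on one of its two limited-efficacy measurements, and does not say how their absence is handled. That the reported rate will describe only those who stayed is an inference from the single survey, since the denominator is not stated.

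The possible size depends wholly on assumed loss. With 14 of 20 surveys and 11 satisfied, the rate over all enrolled is known only to lie between 55% and 85%. With 18 surveys and 14 satisfied, it lies between 70% and 80%. The direction is unknown. The effect on precision (0.22 to 0.26 at 14 responses) is secondary. The feature does not invalidate the pilot, but it weakens what can be concluded on a stated objective.

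**What to change.** - Give the Appendix J survey after the first home mobile assessment, in weeks 2-3, and at a matched time in controls. It should follow that assessment and not be given at the week-2 clinic visit, which comes before any home use.
- Give it again at 24 weeks or at withdrawal, whichever comes first.
- Take the 24-week-or-exit survey as the source of the reported rate. State the number of surveys received out of 20 in each group, with reasons for those missing, and show the week-24 completers separately.
- Add two sensitivity analyses: one using the early survey for patients with no later one, and one counting missing surveys as not satisfied.

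An exit survey cannot reach patients who die, which is why the early survey is needed as well. It is kept out of the main rate because mixing answers given after one home assessment with answers at 24 weeks would blur what is measured, and the mix could differ between groups.

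The cost is a short amendment and one extra brief questionnaire, which can go through the REDCap route that section 4.0 already uses. The downside is slightly more burden for patients, and an early answer that reflects less experience with the device.

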The preoperative and postoperative care for these patients is standardized. The surgical procedure is minimally invasive, performed through 3-4 small incisions, usually no larger than 3cm each. The hospital inpatient recovery is typically for 3-5 days, with regular scheduled postoperative visits at 2-3, 6-7 weeks, and 12-14 weeks from surgery. The timing of this first visit is specified so that a decision can be made as to whether the patient can proceed with additional treatment, such as radiation to the operated extremity, or chemotherapy. The key parts of this assessment include inspecting the surgical wounds for signs of infection and assessing the adequacy of soft tissue healing. In addition, the radiographic studies (x-rays) of the extremity are viewed by the physician. The time required for a surgeon to make this assessment for uncomplicated cases is typically short, averaging 5-7 minutes.

The post-operative follow-up visit utilizes standardized tools to establish patient-centered outcome data with a direct impact on the individual survivor as well as contributing to a dataset for predicting functional outcomes for all bone cancer survivors. However, only one-third of those seen are from local areas, and surveillance of persistent, late effects following surgery is suboptimal. Numerous obstacles limit both the patients' ability to attend face-to-face appointments (cost of travel, impaired mobility), and the providers' ability to collect patient-centered outcome data (clinic capacity). At our clinic, data show that approximately 30% of our patients miss an appointment in the post-operative period. A missed follow-up appointment prevents medical intervention needed to enhance survivorship and reduces data collection, which in turn, makes it difficult to accurately predict outcomes over time for future bone cancer survivors.

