1. The National Institute of Health Patient Reported Outcomes Measurement Information System for General Health (NIH PROMIS GH)⁸⁷ is a validated instrument widely used to assess patients' perceptions of their quality of life. The NIH PROMIS GH is completed by the patient and is composed of eight parameters that include physical functioning, physical role, bodily pain, general health perceptions, vitality, social functioning, emotional role and mental health. The physical function item bank measures self-reported capability rather than actual performance of physical activities. This includes the functioning of one's upper extremities (dexterity), lower extremities (walking or mobility), as well as instrumental activities of daily living, such as running errands. (Appendix G)
2. The Musculoskeletal Tumor Society functional score (MSTS)²⁸ is a validated instrument completed by the clinician to objectively evaluate the functional outcome of patients treated with surgery for the management of tumors of the musculoskeletal system in either the upper or lower extremity. The MSTS assigns numerical values (0-5) to six categories: in the lower extremity, pain, function, emotional acceptance, supports, walking ability, and gait pattern; and in the upper extremity, pain, function, emotional acceptance, hand positioning, manual dexterity, and lifting ability. Normal function corresponds to a score of 30. (Appendix C)

3. The Eastern Cooperative Oncology Group score (ECOG)⁽²²⁾ is a clinician-scored indicator of the cancer survivor's general function using categorical grades as follows: (0) fully active at pre-disease performance without restriction, (1) ambulatory and able to carry out light, non-strenuous work, (2) ambulatory, capable of self-care, up and about more than 50% of waking hours, (3) capable of limited self-care, confined to a chair or bed more than 50% of waking hours, (4) cannot perform self-care, totally confined to chair or bed, and (5) dead. (Appendix D)

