For Specific Aim 1, the mobile device APP used in this study will be developed by the collaborator (e-Health Technology Program). For objective 1 (Specific Aim 2), we will assess the feasibility of mobile device surveillance by comparing whether similar measurements are obtained using the mobile device format versus the established face-to-face format when performed during the same appointment on the same patient. A group of 10 patients who meet the inclusion criteria and have completed the informed consent process will be evaluated by the treating physician and physical therapist face-to-face at the normally scheduled clinic visits (2, 6, 12 and 24 weeks after surgery). After seeing the physician, the patient will then use a mobile device (provided to them with assistance and training from the study coordinator) while still at the clinic for outcome assessment videos. The mobile device data will be provided to independent evaluators (a physician and a

PI: [name], PhD

Protocol: 2015-0966

August 21, 2018

physical therapist who are different from the physician and the physical therapist performing the face-to-face evaluation). The independent evaluators will not have a face-to-face visit with the patient and will use the video sequences to assess the same functional outcomes (MSTS, ECOG, TUG, EVGS, FSST, NIH PROMIS GH).

For feasibility, we are looking for inter-rater agreement on the physician assessed score (defined as less than 10% difference between MSTS scores evaluated using video v face-to-face) for a minimum number of patients (in this step, the MSTS score agreement for a minimum of 70% of the patients. If the feasibility criterion has been met, the research team will move forward to the limited efficacy testing. If feasibility criteria has not been met, the research team will identify the limitations and modify the process, enroll an additional 10 patients and repeat the feasibility assessment.

Specific Aim 3: Limited Efficacy Testing

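### Can the 70%-of-patients MSTS gate fail on attendance alone, even when video and face-to-face scores always agree?

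*Combined protocol and SAP*

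**What the plan says.** Section 4.0 (Specific Aim 1 and 2) has ten patients rated face-to-face at 2, 6, 12 and 24 weeks. At each of these appointments, a second physician and a second physical therapist score the same outcomes from video. Sections 4.0 and 6.0 then state the gate in nearly the same words. Agreement on the MSTS is "defined as less than 10% difference between MSTS scores evaluated using video v face-to-face", and the requirement is "the MSTS score agreement for a minimum of 70% of the patients". If it is not met, the team looks for the limitations, modifies the process, and will "enroll an additional 10 patients and repeat the feasibility assessment". Limited efficacy testing starts "Once the adaptation of the face-to-face follow-up to the mobile format has been verified".

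Three other statements bear on the point:

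- Section 6.0, Limited Efficacy Testing, defines completion for the later phase: "A patient is considered having completed the follow-up assessment if the three outcomes are documented for the 2-, 6-, 12, and 24-week evaluations". The three outcomes are MSTS, TUG and PROMIS.
- Section 2.0 reports that "approximately 30% of our patients miss an appointment in the post-operative period".
- Section 4.0, Outcomes, item 2, gives the scale of the MSTS: "Normal function corresponds to a score of 30".

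**The concern.** With ten patients, 70% means at least 7. A patient may contribute up to four pairs, yet nothing says how the pairs combine into one result per patient, or how a patient with a missing pair is classed. The only place where the plan combines visits within a patient is the completion definition, which needs all four.

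If that rule is carried over to the gate and all ten patients stay in the denominator, the 30% missed-appointment figure leaves about 10 × 0.70 = 7 patients who can qualify. That is exactly the pass mark. The gate could then fail although the two scoring formats never differ, and the team might rework a sound video process and enroll ten more patients for no reason.

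There is a second, smaller gap: the base of the 10% is not given. It could be the face-to-face score or the 30-point maximum.

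**Working it through.** **Plan's own figures.** The plan gives no pass probability for the gate. The two precision figures in Section 6.0 belong to the later phase, and both reproduce:

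- One rate, n = 20: 1.96 × √(0.25/20) = 0.219, stated as 0.22.
- Difference, 20 per group: 1.96 × √(0.5×0.5/20 + 0.7×0.3/20) = 0.297, stated as 0.30.

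**Inputs for the gate.** From the documents: 10 patients, a pass mark of 7, four visits, and about 30% of patients missing an appointment. Assumed: independence between patients, and the per-visit agreement and rater-difference SD used below. The documents give no agreement rate or SD.

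**Step 1: perfect agreement, all four visits required, a missed visit scored as disagreement.** A patient qualifies with probability 1 − m, where m is the share of patients who miss a visit, and P(pass) = P(Bin(10, 1 − m) ≥ 7). At m = 0.30 the terms for 7, 8, 9 and 10 patients are 0.267 + 0.233 + 0.121 + 0.028 = 0.650 after rounding, so P(fail) = 0.350.

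| m | P(pass) | P(fail) |
|---|---|---|
| 0.10 | 0.987 | 0.013 |
| 0.20 | 0.879 | 0.121 |
| 0.30 | 0.650 | 0.350 |
| 0.40 | 0.382 | 0.618 |

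**Step 2: perfect agreement, existing pairs only.** Suppose patients with a missed visit leave the denominator, or each patient is judged on the pairs he or she has (at least one each). Every patient counted then agrees, so P(pass) = 1 whatever m is. The 0.350 comes entirely from scoring absence as disagreement.

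**Step 3: imperfect agreement, no missed visits.** Let a be the per-visit agreement, with visits independent. The patient-level probability is a for one named visit, a⁴ for all four, and a⁴ + 4a³(1 − a) for at least 3 of 4. At a = 0.90 these are 0.900, 0.656 and 0.948.

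| a | One named visit | All four | At least 3 of 4 |
|---|---|---|---|
| 0.80 | 0.879 | 0.062 | 0.910 |
| 0.90 | 0.987 | 0.530 | 0.999 |

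**Step 4: would a stricter written rule remove the problem?** Take the candidate rule that agreement is needed at 3 or more of 4 visits, with a missed visit counted as not agreeing and all 10 in the denominator. If half of the 30% miss two or more visits, only 85% of patients can qualify. With perfect agreement P(pass) = P(Bin(10, 0.85) ≥ 7) = 0.950, so this rule also fails on attendance, 5% of the time. At a = 0.90 with independent visits, when the other half of the 30% miss one visit, the patient-level probability is 0.70 × 0.9477 + 0.15 × 0.729 = 0.773. P(pass) is then 0.83, or about 0.77 if visits within a patient are correlated (intraclass correlation 0.3 or 0.5). The rule would normally be read only after the tenth patient's 24-week visit.

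**Step 5: base of the 10%.** The tolerance is the largest whole number of points below 10% of the base. On the 30-point base it is 2 at every score. On the face-to-face score it is 2 at 21–30, 1 at 11–20 and 0 at 1–10. The readings therefore coincide at 21–30. If all ten patients scored 11–20 and a single visit were used, P(pass) for 1 v 2 points would be 0.97 v 1.00 at an assumed rater-difference SD of 1.0, and 0.26 v 0.86 at 2.0.

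**The case for a change.** The strongest case for a change does not need the borrowed completion rule. Step 3 shows that the pass probability depends heavily on how visits are combined: at 0.80 agreement it runs from 0.06 to 0.91 with no visit missed. Judging existing pairs does not settle this. If 30% of patients miss one visit and agreement is needed at every completed visit, the patient-level probability at 0.90 with independent visits is 0.70 × 0.6561 + 0.30 × 0.729 = 0.678, and P(pass) is 0.59. A rule chosen after the scores are seen could turn one data set into a pass or a fail. This is the only numeric gate before the 40-patient phase, and the wording would cost little.

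The gap itself stands: neither section names a visit, a combining rule, a missed-visit rule or a base. The sensitivity to the reading stands too. But the low figures belong to the strictest reading, agreement at every visit, which the gate does not state. The spread also narrows as agreement rises or as visits within a patient become correlated: at 0.90 with an intraclass correlation of 0.5, all four, one visit and 3 of 4 give 0.89, 0.99 and 0.98.

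The claim that a sound process would be blamed is not supported. Section 6.0 has the team identify the limitations before modifying anything, and poor attendance would be visible as missing pairs.

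**Conclusion.** No change to the plan follows. The arithmetic behind the concern is right, but the 35% failure with perfect agreement needs three steps that the plan does not take: moving a later-phase completion definition to the gate, keeping patients with missed visits in a denominator of ten, and scoring an absent pair as disagreement. Section 4.0 compares two formats within one appointment, and Section 6.0 defines agreement as a difference between two scores. The natural reading is to judge the pairs that exist, and on that reading the failure probability under perfect agreement is 0.

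The 30% is also a loose input. It is a general clinic figure in a paragraph whose standard visits end at 12–14 weeks. It is not specific to consented patients with a caregiver at home, and does not say whether missed visits are rescheduled. The true share may be higher or lower.

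What remains is missing detail in a ten-patient pilot step. No stated rule gives a wrong result. The choice among one visit, several visits or all visits trades speed against strictness, and the 3-of-4 alternative carries its own attendance failure and a late reading. The base of the 10% matters only at face-to-face scores of 20 or less. The stakes are limited: a failed gate brings a review and ten more patients, no clinic visit is removed, and no efficacy estimate depends on it. A sensible analyst would settle the reading before comparing scores and report missed visits apart from disagreement. The assumptions are independence between patients and the agreement rates, correlations and SDs marked above as assumed.
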